2.3.5. Analysis Phases

All data collected from the Baseline visit to the End Point/Early Withdrawal visit (inclusive) will be assigned to the Double-Blind Treatment analysis phase. Data collected prior to the Baseline visit will be assigned to the Screening analysis phase, and data collected after the End Point/Early Withdrawal visit will be assigned to the Post Treatment analysis phase.

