8.1. Incomplete/Missing Dates for Adverse Events

A conservative approach will be used to handle the missing dates for adverse events. The rules for estimating incomplete AE onset dates will be as follows:

- (1) The missing day of the month will be estimated as follows: If the month and year are known and double-blind study medication started during that month then the estimated date is the start date of double-blind study medication. If the month and year are known and double-blind study medication started prior to that month then the estimated date is the 1st day of the month. If the month and year are known and double-blind study medication started after the month, then no estimation will be done, and the AE will not be considered as treatment emergent for the double-blind phase.
- (2) If both the day and the month are missing: No estimation will be performed. However, these AEs will be considered treatment emergent for the double-blind phase and will be included in the double-blind treatment summaries, except for the calculation of duration of the AE. Attempts will be made to get at least the month for the adverse events.

The rules for estimating incomplete AE onset times will be as follows:

The missing times will be estimated as follows: use time 00:00:00 of the given/imputed date for the start date/time of an AE and use 23:59:59 for the end date/time of an AE.

For incomplete AE resolution dates, the rules are:

- (3) The missing day of the month will be estimated as follows: If the month and year are known and the study medication was stopped before, or during that month, the estimated date is the last day of the month or the end of the double-blind phase, whichever is earlier. If the study medication stopped after that month then the estimated date is the last day of the month.

If both the day and the month are missing: the estimated resolution date is the end of the double-blind phase.

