8.2. Adverse Events

The verbatim terms used in the CRFs by the investigator to identify adverse events (AEs) will be coded using the current Medical Dictionary for Regulatory Activities maintained by the sponsor.

Therapeutic reach is the number of days after the last dose intake that a subject is still considered to be potentially affected by study drug. For JNJ42165279, therapeutic reach is defined as 4 days. AEs will be summarised using the therapeutic reach. Therapeutic reach will only be applied to the end of double-blind treatment period or to subjects who discontinue.

A treatment-emergent AE (TEAE) is an event that is new in onset or increased in severity following treatment initiation. Any event with a start date and time after the first dose intake will be considered treatment-emergent. An event that starts prior to and ends after the initiation of study medication will be considered treatment-emergent only if the severity increases after the start of medication. An event that starts in the follow up period but within the therapeutic reach of 4 days will be considered treatment-emergent. Adverse events with onset date during the follow-up phase outside the therapeutic reach of 4 days will be summarized separately.

The number (%) of subjects with TEAEs will be summarized by system organ class and preferred term for each treatment group. A summary will be created for the most common TEAEs ($\geq 5\%$ incidence in either treatment group). In addition, TEAEs will be summarized by severity and relationship to study drug for each treatment group by system organ class and preferred term. For the summaries of AEs by severity/relationship to study drug, the observation with the most severe occurrence/closest relationship to study drug will be chosen if there is more than one incident of an adverse event reported during the treatment phase by the subject.

TEAEs will also be summarized by sex, by country, and by enrollment prior to/after study suspension.

Serious AEs (SAEs) and TEAEs that lead to study discontinuation will be summarized separately by treatment group, system organ class and preferred term.

Treatment-emergent headaches, TEAEs related to liver function test abnormalities and TEAEs of special interest (diplopia, vision impairment, gait disturbance, severe headache) will be presented graphically over time for each individual subject.

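### SAP 8.1 caps incomplete AE resolution dates at the end of the double-blind phase with no lower bound, so an imputed resolution can precede the recorded month or the onset

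*SAP*

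**What the plan says.** SAP Section 8.1 opens with its aim: "A conservative approach will be used to handle the missing dates for adverse events". Rule (3) then deals with incomplete resolution dates.

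- **Day missing.** The condition is "If the month and year are known and the study medication was stopped before, or during that month". In that case "the estimated date is the last day of the month or the end of the double-blind phase, whichever is earlier". If medication stopped after the known month, the last day of that month is used with no cap.
- **Day and month missing.** Here "the estimated resolution date is the end of the double-blind phase".

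The incomplete-onset rule has no matching cap. Where "double-blind study medication started prior to that month then the estimated date is the 1st day of the month", the imputed onset can fall after the double-blind phase.

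Section 2.3.5 fixes the end of the phase by a visit: "All data collected from the Baseline visit to the End Point/Early Withdrawal visit (inclusive) will be assigned to the Double-Blind Treatment analysis phase".

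Section 8.2 brings later events into scope: "An event that starts in the follow up period but within the therapeutic reach of 4 days will be considered treatment-emergent". Events with later onset in follow-up are summarised separately, and the listings cover events that start after treatment. Headaches, liver-test events and TEAEs of special interest "will be presented graphically over time for each individual subject".

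**The concern.** The cap is reasonable only if events are followed no further than the end of the double-blind phase. They are followed further: AEs are collected through the follow-up visit (Protocol 12.3.1), which falls 7 to 28 days after the last dose (SAP 1.2). For an event that outlasts the phase, the rule replaces a later recorded month with an earlier date. For an event that starts after the phase, it puts the end before the beginning. Both results come from applying the rule exactly as written, so this is an error in the rule and not a missing detail.

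At stake is how persistence after stopping drug is described. The protocol identifies a reversible rise in liver transaminases as a safety signal (16.1) and names neurological and visual events of interest (12.2). An imputed resolution at the end of the phase can make an event appear to have stopped with the drug when the site recorded otherwise.

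**Working it through.** The plan gives no figure to reproduce, so the rule is applied to dates.

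**Inputs.** Resolution, onset and treatment-emergence rules: SAP 8.1 and 8.2. End of phase: SAP 2.3.5. Follow-up 7 to 28 days after last dose: SAP 1.2. The SAP gives no formula for AE duration; resolution minus onset plus 1 is assumed here.

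**Formula.** If medication stopped before or during the recorded month, imputed resolution = min(last day of month, end of phase).

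**Main example.** Assume last dose and end of phase are both 10 March. Onset is 12 March, within the 4-day reach and so treatment-emergent. Resolution is recorded as April, day unknown.

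- Imputed: min(30 April, 10 March) = 10 March, before both the recorded month and the onset.
- Duration: 10 March - 12 March + 1 = -1 day.
- Latest scheduled follow-up: 10 March + 28 days = 7 April. Resolution within that window lies between 1 and 7 April.
- Shortest duration: 1 April - 12 March + 1 = 21 days. Longest: 7 April - 12 March + 1 = 27 days.
- The resolution date is therefore 22 to 28 days too early.
- If only the year were recorded, the second rule would also give 10 March, again before onset.

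**Further cases.** Last dose and end of phase are again assumed equal.

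| End of phase | Onset | Resolution | Imputed | Result |
|---|---|---|---|---|
| 25 May | 10 May | June | 25 May | Before the recorded month; duration 16 days |
| 25 May | 3 June | June | 25 May | Before month and onset; duration -8 days |
| 10 May | 20 May | May | 10 May | Month respected, but before onset; duration -9 days |
| 25 May | 20 May | May (true date 24 May) | 25 May | No conflict; duration 6 days |

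**Calendar enumeration.** The rule was run over 365 possible Day 1 dates, with dosing and phase both ending on Day 84, for events resolving after the phase with the day missing. The two columns take last contact at 7 and at 28 days.

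| Conflict | 7 days | 28 days |
|---|---|---|
| Resolution before the recorded month | 13% | 48% |
| Resolution before a fully known onset after the phase | 100% | 100% |
| Resolution before an onset after the phase that is itself imputed | 10% | 33% |

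Moving the cap 4 days later, to allow for the reach, lowers these to 3% and 35%, 21% and 74%, and 1% and 21%. The fault shrinks but remains. These are shares of equally weighted date combinations, not expected AE frequencies.

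**The case against.** The best defence is that the rule seldom does harm. It needs an incomplete resolution date on an event that ended after the phase, and CRF data are queried (Protocol 17.5, 17.6). The documents give no rate of partial dates, so the number affected is unknown and may be small. That stands.

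Four stronger readings are tempting, and the documents do not support them.

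- *The cap always overrides the recorded month.* It does not. Rule (3) also covers medication stopped during the month, when the phase end will normally fall inside it. The phase ends at a visit, not at last dose, so a late early-withdrawal visit can also fall inside the recorded month.
- *Every event in the reach or in follow-up resolves before it starts.* This needs an incomplete resolution date and an onset after the phase ended. For a subject who stops drug before the early-withdrawal visit, part of the reach can lie within the phase. Equating last dose with phase end suits completers, who take the Week 12 dose at that visit (Protocol 9.1.3), but not every early stopper.
- *The example event could have lasted up to 50 days.* That takes resolution on 30 April, beyond the last scheduled follow-up on 7 April. The protocol provides longer follow-up only in particular circumstances, such as persisting clinically significant abnormalities (9.2) and unresolved serious events (12.3.2).
- *The AE tables and plots will be wrong.* SAP 8.2 specifies no duration table and does not say that the plots use imputed resolution dates. Duration is mentioned only in passing, in Section 8.1.

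**Conclusion.** The point holds as a minor but definite error. When the double-blind phase ended before the recorded resolution month, the imputed date precedes that month. When the event began after the phase and its resolution date is incomplete, imputed resolution precedes onset. In both situations an event that outlasts treatment is shortened, which is the opposite of conservative.

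In the example the resolution date is 22 to 28 days early. This rests on last dose and phase end coinciding and on resolution within the scheduled follow-up; the error is larger only if the event was followed beyond that.

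The consequence is confined to AE durations and to whichever listings or per-subject plots use imputed dates. Treatment-emergent status depends on onset and severity, so TEAE incidence is unaffected, and so is efficacy.

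**What to change.** Replace both parts of rule (3) in SAP 8.1.

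- **Day missing, month and year known:** remove the cap at the end of the double-blind phase. Impute the earlier of the last day of the known month and the last AE follow-up contact, counting contacts after Visit 10. Never impute a date before the later of the onset date and the first day of the known month.
- **Day and month missing:** impute the last AE follow-up contact, kept within the recorded year if that is known, and never before onset.

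The bound at the first day of the month is needed as well as the bound at onset. In the main example the follow-up visit could fall anywhere from 17 March to 7 April. If last contact were taken as that visit and it fell on 17 to 31 March, a rule bounded only at onset would still put an April resolution in March. With both bounds neither conflict can arise: with last contact on 7 April, min(30 April, 7 April) = 7 April, which is after both 12 March and 1 April.

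The cost is a few sentences in the SAP and the matching change to the date derivation. The last AE follow-up contact date must be available in the analysis data, including contacts after Visit 10. No hypothesis test or analysis set changes.

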8.2. Adverse Events

The verbatim terms used in the CRFs by the investigator to identify adverse events (AEs) will be coded using the current Medical Dictionary for Regulatory Activities maintained by the sponsor.

Therapeutic reach is the number of days after the last dose intake that a subject is still considered to be potentially affected by study drug. For JNJ42165279, therapeutic reach is defined as 4 days. AEs will be summarised using the therapeutic reach. Therapeutic reach will only be applied to the end of double-blind treatment period or to subjects who discontinue.

A treatment-emergent AE (TEAE) is an event that is new in onset or increased in severity following treatment initiation. Any event with a start date and time after the first dose intake will be considered treatment-emergent. An event that starts prior to and ends after the initiation of study medication will be considered treatment-emergent only if the severity increases after the start of medication. An event that starts in the follow up period but within the therapeutic reach of 4 days will be considered treatment-emergent. Adverse events with onset date during the follow-up phase outside the therapeutic reach of 4 days will be summarized separately.

The number (%) of subjects with TEAEs will be summarized by system organ class and preferred term for each treatment group. A summary will be created for the most common TEAEs ($\geq 5\%$ incidence in either treatment group). In addition, TEAEs will be summarized by severity and relationship to study drug for each treatment group by system organ class and preferred term. For the summaries of AEs by severity/relationship to study drug, the observation with the most severe occurrence/closest relationship to study drug will be chosen if there is more than one incident of an adverse event reported during the treatment phase by the subject.

TEAEs will also be summarized by sex, by country, and by enrollment prior to/after study suspension.

Serious AEs (SAEs) and TEAEs that lead to study discontinuation will be summarized separately by treatment group, system organ class and preferred term.

Treatment-emergent headaches, TEAEs related to liver function test abnormalities and TEAEs of special interest (diplopia, vision impairment, gait disturbance, severe headache) will be presented graphically over time for each individual subject.

Data listings will be generated for all AEs, deaths, other serious SAEs, severe AEs and discontinuations due to AEs. These listings will not be limited to TEAEs but will also include any adverse events with onset before the start of study treatment or after the end of study treatment.

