male	0.24	0.55
female	0.28	0.5

Graphical presentations will be created for the following liver function tests: alanine aminotransferase, aspartate aminotransferase, albumin, bilirubin, alkaline phosphatase, gamma glutamyl transferase. Liver function test results standardized to the upper limit of normal (based on central laboratory ranges) will be graphically presented over time for each subject. The incidence of liver function tests above the central laboratory normal limit will be presented by treatment group at each scheduled time point, at endpoint, and at any time during the double-blind treatment phase.

Graphical presentations will also be created for prothrombin international normalized ratio results.

Clinical laboratory tests that meet the criteria for abnormal and markedly abnormal will be listed by subject.

Results on urine drug screen, alcohol screen and pregnancy test will be presented in a listing.

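### Is a 4-day therapeutic reach too short for counting adverse events, given residual FAAH inhibition 96 hours after the last dose?

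*SAP*

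**What the plan says.** SAP 8.2 defines the concept as follows: "Therapeutic reach is the number of days after the last dose intake that a subject is still considered to be potentially affected by study drug". It then fixes the length: "For JNJ42165279, therapeutic reach is defined as 4 days". On where it applies, the section adds: "Therapeutic reach will only be applied to the end of double-blind treatment period or to subjects who discontinue".

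Any event starting after the first dose is treatment-emergent under the general rule. Events starting in follow-up count if they fall within the reach. For the rest: "Adverse events with onset date during the follow-up phase outside the therapeutic reach of 4 days will be summarized separately".

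Two other outputs in SAP 8.2 matter. Serious events have their own table: "Serious AEs (SAEs) and TEAEs that lead to study discontinuation will be summarized separately by treatment group, system organ class and preferred term". The adverse event listings are broader still: "These listings will not be limited to TEAEs".

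SAP 2.3.5 (Analysis Phases) sets the phase boundary: "All data collected from the Baseline visit to the End Point/Early Withdrawal visit (inclusive) will be assigned to the Double-Blind Treatment analysis phase". Data after that visit belong to the post-treatment phase.

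Protocol 9.1.4 places the follow-up visit 7 to 28 days after the last dose.

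**The concern.** The definition speaks of subjects who may still be affected by the drug, and the protocol's own Phase 1 data show a measurable effect at exactly the point where the window closes. Protocol 1.1 gives residual FAAH inhibition and raised plasma fatty acid amides at 96 hours. Protocol 3.2 (Rationale for Dose Selection) expects covalent binding to make the pharmacodynamic effect outlast the plasma level. Nothing in either document reconciles 4 days with this.

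Safety is the first secondary objective. Follow-up events after day 4 would be missing from the tables by organ class, severity and relationship, and from the plots of headache, liver-related events and events of special interest. Scheduled data are also thinner in that period. Follow-up laboratory tests and ECGs are done only after a Week 12 abnormality (Time and Events Schedule, footnote h), and no neurological examination is scheduled. A late excess on active drug could then be harder to see.

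A second worry concerns subjects who stop treatment early. The reach runs from the last dose, whereas the double-blind phase runs to the Early Withdrawal visit, so two programmers might count differently.

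**Working it through.** The 4 days is a bare definition, so there is no plan figure to reproduce. The check compares it with the documents' other numbers.

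**Inputs**
- Reach: 4 days (SAP 8.2), which is 4 × 24 = 96 h.
- Mean white-cell FAAH activity 96 h after the last dose: 28.3% to 58.2% of predose (Protocol 1.1, study 42165279EDI1002).
- Mean nadir activity after 10 days of dosing: 0.58% to 10.5% (same place).
- Plasma fatty acid amides at 96 h: 1.3 to 3.1 times predose (same place).
- Cohorts: four, each with six subjects on active drug, at 25, 75, 100 and 100 mg (same place).
- Mean plasma half-life: 4.84 to 14.4 h over single doses of 2.5 to 250 mg (Protocol 1.1, study 42165279EDI1001).
- Follow-up visit: 7 to 28 days after the last dose (Protocol 9.1.4).

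**Residual inhibition** = 100 − activity remaining
- At nadir: 100 − 10.5 = 89.5% to 100 − 0.58 = 99.4%.
- At 96 h: 100 − 58.2 = 41.8% to 100 − 28.3 = 71.7%.

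These are ranges of cohort means over 25 to 100 mg, from 4 × 6 = 24 active subjects. The nadir and 96 h ends are not paired by cohort, so no recovery rate can be derived, and the 25 mg value cannot be picked out.

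**Plasma clearance** = 96 / half-life
- 96 / 14.4 = 6.7 half-lives, leaving 0.5^6.67, about 1% of drug (assuming decline at that half-life throughout).
- 96 / 4.84 = 19.8 half-lives, leaving essentially none.

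Four days fits a clearance basis comfortably, although the SAP does not say that this is its basis.

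**Follow-up beyond the reach** = visit day − 4
- 7 − 4 = 3 days to 28 − 4 = 24 days.

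For a subject who stops early, footnote b of the schedule also lets follow-up be timed from early withdrawal, so the span is not exact for them.

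**Where an event after day 4 of follow-up appears**
- Main treatment-emergent tables and event plots: no.
- Separate post-reach summary: yes (SAP 8.2).
- Listings of all, serious and severe events, and of discontinuations due to events: yes (SAP 8.2).
- Serious event table: the wording does not limit serious events to treatment-emergent ones.
- Liver test values: standardized results "will be graphically presented over time for each subject" (SAP 8.3), with no adverse event window attached.
- Diplopia, vision impairment, gait disturbance and severe headache: each triggers an examination and a narrative (Protocol 12.2).

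**Anchor for early stoppers.** Suppose the last dose is on day D and the Early Withdrawal visit on D+10.
- Event on D+6: after first dose, so treatment-emergent. It precedes the visit, so under SAP 2.3.5 it is not in follow-up, and the separate-summary rule does not touch it. It is counted.
- Event on D+12: in follow-up and beyond D+4. It is summarized separately.

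If the visit were instead on D+1, an event on D+3 would be in follow-up but within D+4, and would be counted. Each event has one place. The other reading, a hard cut at D+4, would leave the D+6 event in neither summary, which argues against it.

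**The case for a change.** The strongest counter-argument rests on the definition. It concerns possible effect on the subject, and plasma half-life is a poor yardstick for a covalent inhibitor. If the 25 mg cohort lies within the reported range, as the text reads, its mean inhibition at 96 h was at least 41.8%. The trial cannot settle the matter itself, because the last fatty acid amide sample is at Day 84 or early withdrawal (SAP 7). No table shows all events by arm from first dose through follow-up, and the layout of the separate summary is not specified. A rationale and one extra output set would cost little.

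Part of this stands. The basis for 4 days is unstated, and the residual pharmacodynamic effect is not discussed. The rest carries less weight:

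- A white-cell enzyme level or a plasma lipid is a marker, and the documents link neither to adverse events at that time. The remark in Protocol 3.2 about a longer pharmacodynamic half-life concerns cover across the once-daily dosing interval.
- The Phase 1 transaminase rises on active drug were at 100 mg, with none in the 25 mg cohort, and they returned to normal after dosing stopped (Protocol 1.1).
- A combined table would add off-drug background events over unequal follow-up in both arms, which blurs the on-drug comparison. A reader can already set the main and separate summaries side by side and use the listings for any subject with the same event in both periods.
- Thin scheduled testing at follow-up is a matter of data collection, which repeated tables cannot repair. Everyone still has a physical examination and vital signs at that visit, and persisting abnormalities are followed to resolution or stability (Protocol 9.2).

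**Conclusion.** The concern does not call for a change. The 4-day value lacks a stated basis and meets, without comment, Phase 1 data showing 41.8% to 71.7% residual enzyme inhibition at the same time point. That is an unexplained choice; it does not show that the choice is wrong. Moving the boundary or repeating the tables would only re-display events that the plan already reports, and the reach is the same in both arms. The anchor question is answered by reading SAP 8.2 with SAP 2.3.5, so an analyst would fill the remaining gap in one way. The separate post-reach summary would naturally be produced by arm, as the other adverse event summaries are.

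The calendar span affected is 3 to 24 days per subject. The effect on event counts cannot be computed from the documents, and no delayed excess is documented. The conclusion assumes that the separate summary and full listings are produced as SAP 8.2 says, that the summary is shown by arm, and that events through the Early Withdrawal visit are kept as treatment-emergent. If that summary were dropped, or shown only for both arms together, the point would deserve another look.

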# 3.3. Stopping Criteria

# 3.3.1. Individual Stopping Criteriaa

In this phase 2a safety study, the following individual stopping rules will apply:

- The investigator or sponsor believes (e.g. that for safety or tolerability reasons such as a serious adverse event at least possibly related to the study drug) it is in the best interest of the subject to discontinue the study.
- The subject becomes pregnant

<sup>a This section has been amended per Amendment INT-1.

- A subject will be discontinued from the study when the QTc interval is higher than 500 msec. ECG events should be confirmed by repeat twice as soon as possible after the initial ECG, and the average value of the QTcB interval will be used to determine whether a subject should be discontinued. The subject will continue to be monitored by repeated 12-lead ECGs (at least every 60 min) until the ECG normalizes.
- Because of limited information on the effects of JNJ-42165279 on the human liver function a subject will be discontinued from the study if either of the following occur:
  - Aspartate transaminase (AST) and/or alanine transaminase (ALT) >3 x Upper Limit of Normal (ULN) (confirmed by repeat),
  - Total bilirubin >2 x ULN (confirmed by repeat).

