# 10.2. Discontinuation of Study Treatment

If a subject's study treatment must be discontinued before the end of the treatment regimen, this will not result in automatic withdrawal of the subject from the study.

A subject's study treatment should be discontinued if:

• The investigator believes that for safety reasons (e.g., adverse event) it is in the best interest of the subject to discontinue study treatment

- A subject experiences a severe or serious adverse event while receiving treatment, that is considered at least possibly related to study drug
- Noncompliance with study drug (i.e. less than 80% compliance) during the blinded treatment phase

If a subject discontinues study treatment before the end of the blinded phase the subject will be asked to complete the End-Of-Treatment Visit (Week 12 assessments) if not obtained earlier and the Follow-up visit as per Time and Events Schedule.

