## 10.3. Withdrawal from the Study

A subject will be withdrawn from the study for any of the following reasons:

- It is not possible to obtain blood
- Serious violation of protocol procedures
- Lost to follow-up
- Withdrawal of consent

If a subject is lost to follow-up, every reasonable effort must be made by the study site personnel to contact the subject and determine the reason for discontinuation/withdrawal. The measures taken to follow-up must be documented.

When a subject withdraws before completing the study, the reason for withdrawal is to be documented in the CRF and in the source document. Study drug assigned to the withdrawn subject may not be assigned to another subject.

Any subject who withdraws after receiving the study drug will be asked, if not yet obtained, to have the Week 12 assessment performed. In addition the subjects should have a follow-up evaluation as described in Section 9.1.4.

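### SAP 8.2 ties its adverse-event discontinuation table to leaving the study, while the protocol partly treats adverse events as grounds for stopping drug only, so the by-arm count of drug stops could be incomplete

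*SAP*

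**What the plan says.** SAP 8.2 plans one discontinuation table for adverse events: "TEAEs that lead to study discontinuation will be summarized separately by treatment group, system organ class and preferred term". The SAP has no matching table for events that lead to discontinuation of study treatment.

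Protocol 10.2 deals with stopping treatment. When treatment is stopped early, "this will not result in automatic withdrawal of the subject from the study". Two of its reasons concern adverse events: "The investigator believes that for safety reasons (e.g., adverse event) it is in the best interest of the subject to discontinue study treatment" and "A subject experiences a severe or serious adverse event while receiving treatment, that is considered at least possibly related to study drug". Protocol 10.3 deals with leaving the study. It opens "A subject will be withdrawn from the study for any of the following reasons" and gives four: blood cannot be obtained, a serious protocol violation, loss to follow-up and withdrawn consent. An adverse event is not among them.

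Other protocol sections draw the line elsewhere. Section 3.3.1 ends study participation when the investigator or sponsor believes, for example on safety or tolerability grounds, that "it is in the best interest of the subject to discontinue the study". Its QTc rule reads "A subject will be discontinued from the study when the QTc interval is higher than 500 msec", and for confirmed liver findings "a subject will be discontinued from the study if either of the following occur". Section 16.1 describes the liver rule as one for stopping treatment. Section 10.1 says that anyone who stops treatment early has not completed the study.

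**The concern.** Safety and tolerability form a secondary objective in both documents. How many subjects in each arm stopped drug because of an adverse event, and which events were responsible, is a basic tolerability result. The protocol separates stopping drug from leaving the study, and the SAP table counts only the second. If a site stops drug under 10.2 and does not record a study withdrawal, that subject's event falls outside the table when the SAP is applied as worded. Inclusion would then turn on how the exit was labelled and not on whether the drug was stopped. Such events are likely to be few, so one or two labelled differently could alter the comparison between arms.

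**Working it through.** The plan states no figure to reproduce, and the point is one of definition. The check sets the passages side by side.

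**1. What ends, by trigger and section**

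| Trigger | Section | What ends |
|---|---|---|
| Safety judgement that stopping is in the subject's interest | Protocol 3.3.1 | Study |
| Much the same judgement | Protocol 10.2 | Treatment |
| Serious event, at least possibly related | Protocol 3.3.1 (as an example) | Study |
| Severe or serious event, at least possibly related | Protocol 10.2 | Treatment |
| Confirmed transaminase or bilirubin elevation | Protocol 3.3.1 | Study |
| Liver rule as restated | Protocol 16.1 | Treatment |
| QTc above 500 msec | Protocol 3.3.1 | Study |

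The safety judgement, the related serious event and the liver rule each appear under both descriptions. A related event that is severe but not serious is named only in 10.2; it reaches 3.3.1 only through the general judgement.

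**2. Apply SAP 8.2 literally**

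- Drug stopped under 10.2, no study withdrawal recorded: outside the table.
- The same stop handled under 3.3.1: inside the table.
- The same stop recorded as study discontinuation because 10.1 makes the subject a non-completer: inside the table.

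The documents do not settle which applies. That depends on the case report form, which is not part of them.

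**3. Does visit attendance tell the two groups apart?** No. Section 10.2 asks treatment stoppers for the Week 12 assessments and the follow-up visit. Section 10.3 asks the same of withdrawn subjects who have received drug. The Time and Events Schedule calls the stoppers' visit an early-withdrawal visit.

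**4. What the SAP reports elsewhere**

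- SAP 8.2 tabulates all treatment-emergent events by arm, system organ class and preferred term, and also by severity and relationship to drug. These tables do not show which events stopped the drug.
- SAP 8.2 lists discontinuations due to adverse events, with no restriction to study discontinuation. A listing gives no rate by arm.
- SAP 4.2 gives discontinuations and termination reasons by arm, without system organ class or preferred term. It refers to completing treatment, to study termination and to time to treatment discontinuation, so the terms are not aligned within the SAP either.

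**5. Weight of one missed subject**

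- Enrolment is 137 with 1:1 allocation (Protocol 3.1). The safety set keeps every dosed subject (SAP 2.5.4).
- If all are dosed and split evenly, the arm size is 137 / 2 = 68.5.
- One subject is 1 / 68.5 = 1.46%, or about 1.5 percentage points.
- SAP 1.2 and 1.4 still carry 122 subjects, 61 per arm. On that basis one subject is 1 / 61 = 1.64%, or about 1.6 points.

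The 15% drop-out allowance in Protocol 11.2 and SAP 1.4 is not split by reason. The documents therefore give no count of adverse-event stops and no count of those that would be missed.

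**The case against.** The strongest reply is that stopping drug and leaving the study nearly coincide in this trial. Section 3.3.1 ends participation for safety, QTc and liver reasons, and its general safety trigger is close to the first adverse-event reason in 10.2. Most stops under 10.2 could therefore also be handled under 3.3.1. Section 10.1 makes every early stopper a non-completer, and both groups are asked for the same visits. Section 10.3 is not the full list of exits either: 4.3 adds a positive drug screen and 12.3.3 adds pregnancy. The absence of adverse events from 10.3 therefore proves little on its own. Finally, the SAP still tabulates every treatment-emergent event and lists discontinuations due to adverse events.

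Most of this stands, and it limits the point. A reader might infer that under this protocol an adverse event stops only treatment and never participation, so that the table would be largely empty. Section 3.3.1 contradicts that. A reader might also infer that a subject who attends the exit visits cannot be a study discontinuation. Section 10.3 contradicts that.

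The reply does not remove the ambiguity. Section 10.2 states plainly that stopping treatment is not automatic withdrawal. Whether such a subject is recorded as discontinued from the study rests on a recording convention that neither document states.

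**Conclusion.** The point holds as a definitional gap of minor severity. SAP 8.2 keys its only by-arm table of adverse-event discontinuations to leaving the study, and the protocol is inconsistent on whether an adverse event ends treatment or participation. The count of adverse-event drug stops by system organ class and preferred term could be incomplete. The documents do not show that it will be, and they do not support a stated undercount. Each missed subject would be worth about 1.5 percentage points, assuming 137 dosed subjects split evenly. No event disappears from the report, and no primary analysis, analysis set or test is affected.

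**What to change.** In SAP 8.2, define the table as treatment-emergent events leading to discontinuation of study treatment. Identify them from the reason for early discontinuation of study drug, which Protocol 17.4 already requires in source documents, and confirm that the case report form captures it. Show separately the subjects who also left the study. Use the same term for the listing in 8.2 and for the disposition summaries in SAP 4.2.

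Protocol 3.3.1, 10.1 to 10.3 and 16.1 must be reconciled on whether each trigger ends treatment or study participation. This concerns consistent wording and recording; no clinical rule needs to change for the table to be well defined.

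The cost is about one sentence in the SAP and one extra row or table. The reported discontinuation rate may look slightly less favourable.
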